5.2.3 Sensitivity analyses

A sensitivity analysis of the prevalence of injuries (primary outcome in publication 1) will be performed with a mixed effect logistic regression model where only the June measurement is used as an outcome. The model will have a fixed effect for group (intervention vs control) and a random intercept for club to account for the clustering of gymnasts within clubs.

STATISTICAL ANALYSIS PLAN for NCT05506579

A sensitivity analysis of the bother of UI (primary outcome in publication 2) will be performed with a quantile (median) regression model with the June measurement as dependent variable and group (intervention vs control) and the baseline (Oct) measurement as independent variables.

6 Statistical Software

All statistical analyses will be done in Stata version 17 (StataCorp LLC, College Station, TX, USA).

7 References

Clarsen, B., et al., *The Oslo Sports Trauma Research Center questionnaire on health problems: a new approach to prospective monitoring of illness and injury in elite athletes*. British journal of sports medicine, 2014. 48(9): p. 754-760.

Clarsen, B., et al., *Improved reporting of overuse injuries and health problems in sport: an update of the Oslo Sport Trauma Research Center questionnaires*. British Journal of Sports Medicine, 2020. 54(7): p. 390-396.

Ferreira, S., et al., Reeducation of pelvic floor muscles in volleyball athletes. Revista da Associação Médica Brasileira, 2014. 60(5): p. 428-433

Olsen, O.-E., et al., Exercises to prevent lower limb injuries in youth sports: cluster randomised controlled trial. BMJ, 2005. 330(7489): p. 449.

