2.1 Trial Design

This is an assessor blinded cluster randomized controlled trial with rhythmic gymnastics clubs as the unit of randomization. Two different interventions (preventive exercises for the knees, lower back and hip/groin and pelvic floor muscle training (PFMT)) for two different conditions (overuse injuries and UI) are combined in this design. After inclusion, all rhythmic gymnastics clubs will be randomly allocated 1:1 to preventive exercises for knee, lower back and hip/groin and PFMT or a control group with no intervention.

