2.2 Randomisation

Eligible rhythmic gymnastics clubs are allocated in a 1:1 ratio between preventive exercises for knee, lower back and hip/groin and PFMT (intervention group) or a control group with no intervention, using a computer randomization procedure stratified by club size (less than 10 gymnasts/10 or more gymnasts). The randomization is blocked within each stratum, with block sizes 4 and 6 in random order.

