2.3 Sample size

The power calculation for Publication I (overuse injuries) is based on average prevalence in our previous study (Gram, M., Clarsen, B., & Bø, K., 2021) and previous studies with a

STATISTICAL ANALYSIS PLAN for NCT05506579

similar design (Olsen, et.al, 2005). With 80% power, 5% significance level and a decrease in the primary outcome measure from 40% to 20% in the intervention group and no change in the control group at least 158 gymnasts are required. In addition, to account for randomization at the cluster level, the total number were multiplied with an inflation factor (DE) of 1.4 (based on the following assumptions; average number of gymnasts per club (cluster) $m = 9$, $ICC = 0.05$, $DE = 1+(m - 1)*ICC = 1+(9 - 1)*0.05 = 1.4$), resulting in a required total sample size of 220 gymnasts (110 in each group).

The power calculation for Publication II (UI) is based on average prevalence in our previous study (Gram, M., & Bø, K., 2020) and studies with a similar design (Ferreira, et.al, 2014). With 80% power, 5% significance level and a decrease in the total sum score of ICIQ from 4.7 to 2.5 (SD 2.1) in the intervention group and no change in the control group at least 30 gymnasts are required. Multiplied with the same DE, the total required sample size will be 42 gymnasts (with 21 in each group).

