2.4.2 Decision Rule

This RCT is designed to address a single primary outcome for each publication. Superiority of the intervention is claimed if the primary null hypothesis is rejected on the significance level (alpha) of 0.05 (two-sided).

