5.2 Analysis Methods

5.2.1 Publication 1

The outcomes prevalence of overuse injuries (primary outcome) and prevalence of substantial overuse injuries (secondary outcome) will be analyzed with multilevel mixed effect logistic regression models. The models will be fitted with outcome data from all time points (Nov, Dec, ..., June) except the baseline (Oct). The models will have a fixed effect for group (intervention vs control) and two random intercepts: gymnast and club, with gymnast nested within club. Based on the fitted model, we will present the odds ratio (OR) for injury (with 95% confidence interval [CI]) for intervention vs control and the P-value for the null hypothesis of an OR = 1.

The observed prevalence of injuries (with 95% CI) for each time point (Oct, Nov, ..., June) for the primary outcome and the secondary outcome I) and II) will be presented in a figure.

Self-experienced effect and progress is measures on a -5 to 5 scale and only measured after end of the intervention (June) and only for the gymnasts in the intervention group. We will present the observed number and percentage of responses in each category (-5, -4, ..., 4, 5) and also the mean and standard deviation of the responses.

5.2.2 Publication 2

Bother of UI (primary outcome) at the end of the intervention (June) will be analyzed with linear regression, with the June measurement as the dependent variable and group (intervention vs control) and the baseline (Oct) measurement as independent variables (ANCOVA). The standard errors in the model will be adjusted for the clustering of gymnasts within clubs. We will present the mean and standard deviation of the baseline and end-of-intervention measurements for each group and the estimated between-group difference in changes from baseline to end-of-intervention with a 95% CI. We will also give the P-value for the null hypothesis of a zero between-group difference.

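### The median-regression sensitivity analysis of UI bother names no allowance for clubs, so it is not a clean check on the cluster-adjusted ANCOVA

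*SAP*

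**What the plan says.** SAP section 2.1 describes a "cluster randomized controlled trial with rhythmic gymnastics clubs as the unit of randomization". Section 2.3 assumes nine gymnasts per club and an ICC of 0.05, giving a design effect of 1.4, and applies that factor to the UI sample size as well as to the injury sample size.

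The between-group models in section 5.2 treat clubs as follows:

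- **Injury outcomes (5.2.1):** random intercepts for gymnast and club.
- **UI bother, primary ANCOVA (5.2.2):** "The standard errors in the model will be adjusted for the clustering of gymnasts within clubs".
- **UI prevalence (5.2.2):** random intercept for club.
- **June-only injury sensitivity analysis (5.2.3):** "a random intercept for club to account for the clustering of gymnasts within clubs".
- **UI bother, median-regression sensitivity analysis (5.2.3):** it "will be performed with a quantile (median) regression model with the June measurement as dependent variable and group (intervention vs control", plus the baseline score. Nothing is said about clubs.

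Section 3.1 requires a two-sided 95% CI for every efficacy estimate. An interval for the median difference will therefore be reported, although 5.2.3 does not itself mention an interval or a P-value.

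**The concern.** A sensitivity analysis is most useful when it alters one assumption and holds the rest. Here the intended change is from a mean to a median. As listed, the model also drops the allowance for clubs that the ANCOVA makes.

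If the two analyses then agree or disagree in precision or significance, the reader cannot tell whether the cause is the choice of summary or the loss of the cluster adjustment. With a positive ICC, which the plan itself assumes for UI, the error goes towards an interval that is too narrow, and so towards apparent confirmation. The silence stands out because the paragraph just before it, on the injury sensitivity analysis, does name the club term.

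**Working it through.** **Inputs from the SAP.** Cluster size m = 9, ICC = 0.05, and UI bother falling from 4.7 to 2.5 with SD 2.1 at 80% power (2.3); two-sided alpha 0.05 (2.4.2); 1:1 allocation of clubs (2.2).

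**Assumption.** The SAP gives no number of clubs. I take 24, from 220/9 = 24.4.

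**Step 1: the plan's own figures.** The difference is 4.7 − 2.5 = 2.2. Per arm, n = 2(1.96 + 0.84)² × 2.1²/2.2² ≈ 14.3, rounded up to 15, so 30 in total. The design effect is 1 + (9 − 1) × 0.05 = 1.4, and 30 × 1.4 = 42. Both stated totals reproduce. The plan therefore already treats clustering as relevant to this outcome.

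**Step 2: large-sample effect of ignoring clubs for a median.** Inference on a median depends on the signs of the residuals. For normal residuals with intraclass correlation ρ, the signs correlate at (2/π)·asin(ρ). The design effect is therefore

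DE = 1 + (m − 1)(2/π)·asin(ρ) = 1 + 8 × 0.637 × 0.0500 ≈ 1.25.

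- Standard error too small by 1 − 1/√1.25 ≈ 11%.
- Actual size of a nominal 5% test: 2·Φ(−1.96/√1.25) ≈ 8.0%.

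**Step 3: simulation.** Two separate simulations fitted the median regression with independence standard errors to a continuous score with no mass at 0 and no group effect, using 24 clubs of 9.

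| Runs per case | Rejection, ICC 0 | Rejection, ICC 0.05 |
|---|---|---|
| 2000 | 4.6% | 6.0% |
| 1500 | 4.2% | 6.5% |

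The Monte Carlo standard errors at ICC 0.05 are √(0.06 × 0.94/2000) ≈ 0.5 points and √(0.065 × 0.935/1500) ≈ 0.6 points. The simulated test was slightly conservative without clustering, which explains part of the gap to 8.0%.

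**Step 4: what happens with many zeros.** The ICIQ-UI-SF sum score runs from 0 to 21 (5.1.1), and the SAP background puts UI at just over 30% of gymnasts, so most scores may be 0. A further simulation used 24 clubs of 9, about 69% zeros, integer scores, a latent baseline–June correlation of about 0.7 and 600 trials per ICC value; all of these apart from the cluster size are assumptions. The fitted group coefficient was 0 in every trial, no trial rejected, and about a third gave no usable standard error. A second check, with 50–69% zeros, gave a coefficient of 0 in nearly every trial and almost no rejections. The percentages in Steps 2 and 3 therefore do not carry over to a score that is mostly 0.

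**The case against.** **The plan is silent; it does not say that clubs will be ignored.** This is true. A reader might infer a decision to drop clustering, and the text does not support that. An analyst could add the adjustment unprompted. But the model is listed with its dependent variable and covariates, no clause extends cluster handling to all models, and a prespecified analysis should not depend on an unprompted addition.

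**The inflation may not occur for this outcome.** This stands. With mostly zero scores the analysis fails differently: it shows a difference of 0 whatever the clustering. The type I figures hold only if zeros are well under half, or for an estimator that replaces the median.

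**The effect is modest and decides nothing.** This also stands. Superiority requires the primary null hypothesis to be "rejected on the significance level (alpha) of 0.05 (two-sided", that test is the cluster-adjusted ANCOVA, and section 2.4.1 calls all other efficacy analyses supportive or exploratory. Omitting a clustered variance changes the standard error and leaves the fitted coefficient as it is, so direction and size can still be read.

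**The monthly injury figure.** A reader might extend the point to section 5.2.1, which promises "The observed prevalence of injuries (with 95% CI) for each time point (Oct, Nov, ..., June"). That does not follow. The SAP names no method for those intervals and does not say that the figure is split by arm. A claim that the bars are too short would rest on silence about a descriptive display.

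**Conclusion.** The point holds as a gap in one supportive analysis. The median regression is the only between-group model in section 5.2 without stated club handling. As listed, its interval and any P-value assume independent gymnasts, so it is not a like-for-like check on the ANCOVA.

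The size is moderate and conditional. At the plan's ICC of 0.05, with 24 clubs of 9 assumed and no large mass at 0, a nominal 5% test runs at about 6–6.5% by simulation and 8.0% by large-sample theory. A reader might apply the plan's design effect of 1.4 directly and get 2·Φ(−1.96/√1.4) ≈ 9.8%. That is the design effect for a mean and overstates the effect on a median. Larger figures would need an ICC that the SAP does not give.

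A reader might also infer that the Publication II conclusion is at risk. It is not, because the primary ANCOVA adjusts for clubs. The correction is worth making because it is nearly free, but no decision depends on it.

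**What to change.** Add one sentence to section 5.2.3: the 95% CI and P-value of the median regression, or of any estimator that replaces it, are obtained from a bootstrap that resamples whole clubs within arm, or from a club-clustered variance. Name which of the two will be used.

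The cost is that sentence and a few lines of code. By the large-sample design effect the interval becomes about √1.25 ≈ 1.12 times as wide at an ICC of 0.05. The design, the data and the primary analysis do not change. The sentence does not make the median informative if most scores are 0. That is a separate matter, and whichever estimator is used here will need the same club-level inference.

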1.1 Background and rationale

Overuse injuries are common among competitive Norwegian rhythmic gymnasts with a mean weekly prevalence of 37% [95% CI: 36% to 39%] and incidence of 4.2 new overuse injuries [95% CI: 3.6 to 4.9] per gymnast per year (Gram, M., Clarsen, B., & Bø, K., 2021). The knees, lower back and hip/groin were the most common injury locations. It has been postulated that reduced physical capacity (e.g strength, flexibility, stability) in the knees, lower back and hip/groin can increase the risk of injuries in rhythmic gymnastics.

In addition, more than 30% of the Norwegian rhythmic gymnasts experience urinary incontinence (UI), and 70% reported that UI negatively affected sports performance (Gram, M., & Bø, K., 2020). Few of the rhythmic gymnasts had any knowledge about the pelvic floor.

Hence, this assessor blinded cluster randomized controlled trial aims to find out whether the implementation of exercises targeting reduced physical capacity and pelvic floor dysfunction can prevent/reduce the prevalence of overuse injuries and UI.

The results from this RCT will be presented in two separate publications: **Publication I** on overuse injuries and **Publication II** on UI.

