3.3 Analysis Populations

The Enrolled set will include all gymnasts who have provided informed consent and have been included into the study data base.

The Full Analysis Set (FAS) will be defined as all gymnasts randomly assigned to either the intervention or control group and who have responded to:

STATISTICAL ANALYSIS PLAN for NCT05506579

- Publication I: The OSTRC-H2 questionnaire either at baseline (Oct 2022) or Nov 2022 + one or more of April, May and June 2023.
- Publication II: The ICIQ-UI-SF questionnaire at baseline and in June 2023.

The Per Protocol Analysis Set (PPS) will include all randomised gymnasts meeting the study eligibility criteria and with no major protocol deviations affecting the intervention efficacy (FAS + completed 65% or more of the intervention sessions per week).

4 Trial Population

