5.1 Outcome Definitions

All outcomes will be analyzed on the full analysis set. An additional analysis of the primary outcome (in both publications) and the secondary outcomes I) (publication I) and I)-III) (publication II) will be performed on the per protocol set.

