5.1.1 Primary Outcome Definition

Publication I: The primary outcome is the prevalence of overuse injuries in the lower back, knees and hip/groin during the intervention period. In the OSTRC-H2 a health problem is defined as: “any condition that you consider to be a reduction in your normal state of full health, irrespective of its consequences on your sports participation or performance, or whether you have sought medical attention. This may include, but is not limited to, injury, illness, pain or mental health conditions.” Furthermore, an overuse injury is defined as: “an injury caused by multiple accumulative bouts of energy transfer without a single, clearly identifiable event responsible for the injury.” (Clarsen, et.al, 2020; Clarsen, et.al 2014). The primary outcome is dichotomous.

Publication II: The primary outcome is the bother of UI before and after the intervention period. Degree of bother is defined with the ICIQ-UI-SF sum score (0-21 points). The primary outcome is continuous.

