5.1.2 Secondary Outcomes Definitions

Publication I: The secondary outcomes are:

- I. The prevalence of substantial overuse injuries in the lower back, knees and hip/groin during the intervention period. A substantial overuse injury is defined as “an overuse injury leading to moderate or severe reductions in sports performance or participation, or time loss” in the OSTRC-H2 (Clarsen, et.al, 2020; Clarsen, et.al 2014). The secondary outcome is dichotomous.
- II. The primary outcome and the secondary outcome number I) including overuse injuries in the calf/ankle/foot in addition to lower back, knees and hip/groin. The same definitions as listed above apply. The secondary outcome is dichotomous.
- III. The self-experienced effect and progress of the exercise program related to overuse injuries in the knees, lower back and hip/groin. The secondary outcome is continuous (score of -5 to 5).

Publication II: The secondary outcomes are:

- I. The prevalence of UI before and after the intervention period. The prevalence is defined by question 6 in the ICIQ-UI-SF. The secondary outcome is dichotomous.
- II. The primary outcome and the secondary outcome number I) restricted to gymnasts having UI. The secondary outcome is continuous.
- III. The primary outcome and the secondary outcome number I) restricted to gymnasts having SUI. The secondary outcome is continuous.

STATISTICAL ANALYSIS PLAN for NCT05506579

IV. The self-experienced effect and progress of the exercise program related to UI.
The secondary outcome is continuous (score of -5 to 5).

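### The median-regression check on UI bother would very probably return a group difference of exactly 0 with or without a benefit, so it cannot test the ANCOVA result

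*SAP*

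**What the plan says.** For Publication II, SAP 5.1.1 defines bother as the ICIQ-UI-SF sum score, 0 to 21. SAP 5.2.2 analyses the June score by ANCOVA on group and October score, with standard errors adjusted for clubs. SAP 5.2.3 adds one sensitivity analysis of this outcome: "quantile (median) regression model with the June measurement as dependent variable and group (intervention vs control) and the baseline (Oct) measurement as independent variables".

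Its population is everyone, continent or not. SAP 5.1 says "All outcomes will be analyzed on the full analysis set", and for Publication II SAP 3.3 makes that set the gymnasts who answered "The ICIQ-UI-SF questionnaire at baseline and in June 2023". The restriction to incontinent gymnasts is a separate secondary outcome in SAP 5.1.2: "The primary outcome and the secondary outcome number I) restricted to gymnasts having UI".

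On how common UI is, SAP 1.1 gives a single figure: "more than 30% of the Norwegian rhythmic gymnasts experience urinary incontinence (UI"). UI status and bother come from different parts of the questionnaire. For UI status, "The prevalence is defined by question 6 in the ICIQ-UI-SF"; the SAP does not say that a gymnast without UI scores 0.

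**The concern.** A sensitivity analysis of a mean difference in a skewed score should be able to come out differently when the treatment works and when it does not. If roughly 60-70% of gymnasts score 0, the median sits on that block of zeros in both arms. The reported difference is then 0 whatever happens to the minority with symptoms.

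Such a result would not show whether the ANCOVA estimate depends on the zero-heavy distribution. Printed beside a significant ANCOVA, it could also be misread as failing to support a real benefit.

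A smaller point: every other regression in SAP 5.2 names a club random intercept or cluster-adjusted standard errors, and this one names neither.

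**Working it through.** **Inputs from the SAP.** UI in more than 30% (1.1). Sum score 4.7 falling to 2.5, SD 2.1; 42 gymnasts required for Publication II and 220 for Publication I; average club size 9, ICC 0.05, design effect 1.4 (2.3). Allocation 1:1 by club, stratified by club size (2.2).

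**Assumptions the SAP does not fix.** Continent gymnasts score 0. UI prevalence is 30-50%. New onset by June is 0, 10 or 20%. Scores in gymnasts with UI are rounded normal, mean 4.7, SD 2.1, with October-June correlation 0.7.

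**The SAP's own figure.** Per arm, 2 × (1.96 + 0.84)² × 2.1² / 2.2² = 14.3, rounded up to 15. That makes 30 in total, and 30 × 1.4 = 42, as stated.

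**Whom 4.7 (SD 2.1) describes.** With 70% zeros, an overall mean of 4.7 needs a mean of 4.7/0.3 = 15.7 among those with UI. The overall SD is then at least 15.7 × √(0.3 × 0.7) = 7.2, far above 2.1. The figures are therefore read as describing gymnasts with UI.

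**Algebra.** For any baseline slope b, each arm's fitted level is the median of (June − b × October). A gymnast scoring 0 both times contributes 0 for every b. If such gymnasts exceed half of each arm, both medians are 0 and the group coefficient is exactly 0. Example: in an arm of 110 with 30% UI and no new onset, 77 score 0 both times. If the other 33 each improve by 2.2 points, the mean falls by 33 × 2.2/110 = 0.66 and the median stays at 0.

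**How often the condition holds.** The share scoring 0 both times is (1 − prevalence) × (1 − onset). Exact binomial, 110 per arm, gymnasts independent:

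| UI | Onset | Share 0 both times | P(over half in both arms) |
|---|---|---|---|
| 30% | 10% | 0.63 | 0.993 |
| 35% | 10% | 0.585 | 0.914 |
| 40% | 0% | 0.60 | 0.958 |
| 40% | 10% | 0.54 | 0.597 |
| 40% | 20% | 0.48 | 0.092 |

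The condition is sufficient, not necessary. Residuals of gymnasts with UI fall on both sides of the block at 0, so the coefficient can be 0 when the condition fails.

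**Simulation.** Exact least-absolute-deviation fits, 600 trials per scenario, ICC 0.05. Designs: 24 clubs of 5-13 (N about 220); 16 clubs of 5-13 (N about 140, since 42/0.30 = 140 yields 42 gymnasts with UI); 6 clubs of 7 (N = 42). Percentage of trials with a coefficient of exactly 0, as a range over the onset rates; benefit means 2.2 points:

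| UI | N≈220, benefit | N≈220, none | N≈140, benefit | N=42, benefit |
|---|---|---|---|---|
| 30% | 99.8-100 | 100 | 99.5-100 | 90.3-100 |
| 35% | 99.8-100 | 100 | not quoted | not quoted |
| 40% | 96.2-100 | 100 | 93.2-100 | 82.2-98.3 |
| 45% | 89.5-100 | 100 | 81.2-99.8 | 69.3-91.5 |
| 50% | 71.2-99.5 | 100 | not quoted | not quoted |

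At N = 42 without benefit the share was 97.7-99.8% at 30% UI and 93.0-99.7% at 40%. Over 30-40% UI at N about 220, the ANCOVA coefficient averaged -0.62 to -1.07 with the benefit and was within 0.01 of 0 without it.

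**Other assumptions.** A separate simulation with 10-20% remission and correlation 0.5 gave 99-100% at N = 220 and 30-40% UI, with and without benefit. Restricted to about 77 gymnasts with UI (35% of 220), the coefficient was 0 in 0% of trials with benefit and 23% without. The failure therefore comes from including the continent majority.

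**Clustering.** A design effect of 1.4 corresponds to a standard-error factor of √1.4 = 1.18.

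**The case against.** Four points can be made for the plan.

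- **The analysis is only supportive.** SAP 2.4 rests superiority on the single primary analysis, so an uninformative extra cannot create a false claim. This stands, and it limits the weight of the point.
- **The result needs assumptions the SAP does not make.** More than 30% has no upper limit, and continent gymnasts might score above 0. This stands in part. When 20% of continent gymnasts were allowed to score above 0, one set of runs still gave 98% exact zeros at 30% UI and 89% at 40%. A harsher set gave 96-100% at 30%, about 75% at 40% with 20% onset, and about 33% at 50% with 20% onset. At the SAP's own figure the conclusion survives; well above it, it weakens.
- **Other planned analyses cover the ground.** UI prevalence, together with bother among gymnasts with UI, comes close to a two-part description of where a mean difference arises. That is useful, as is the per-protocol analysis. None of them, however, tests whether the mean difference in the full analysis set is robust to the zero-heavy distribution.
- **Median regression is conventional for skewed outcomes, and a permutation test checks something else.** True: the replacement checks the p-value and the influence of single clubs, not a different summary. Nor does re-allocation at fixed counts within strata reproduce the blocks of 4 and 6. It remains valid if clubs are exchangeable within strata.

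**Conclusion.** The point holds, on condition. If UI prevalence is about 30-40%, continent gymnasts score 0 and about 220 gymnasts are analysed, the planned median regression returns a group difference of exactly 0 in at least 96% of trials with a 2.2-point benefit and in all simulated trials without one. It cannot separate the two cases and so cannot check the ANCOVA difference.

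The 30% comes from the SAP; the 40% and the zero score are assumptions. The behaviour is less certain at 45-50% UI, in smaller samples, or if many continent gymnasts score above 0. The primary analysis and its claim are unaffected. This is a change worth making to a supportive analysis, and the missing club adjustment is secondary to it.

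**What to change.** Replace the sentence in SAP 5.2.3 with a check of the same ANCOVA coefficient that does not rely on normality and respects the clubs. Possible wording:

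> A sensitivity analysis of the bother of UI will test the ANCOVA group coefficient with a permutation test that re-allocates clubs to the groups within the two club-size strata, keeping the number of clubs per group in each stratum. The range of the coefficient with each club left out in turn will be reported.

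A club-level bootstrap confidence interval is another option.

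The permutation test was tried at N about 220 and 30, 40 and 45% UI (600 trials, 299 permutations each, clubs allocated 1:1 within strata). Without benefit it rejected at the 5% level in 3.8-6.7% of trials, and the mean leave-one-club-out range straddled 0. With benefit that range averaged -0.66 to -0.54 (30% UI, no onset) and -1.18 to -0.97 (40% UI, 20% onset).

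The SAP should state the limits: these checks address the p-value or confidence interval and the influence of single clubs. They do not show whether a few high scores spread over several clubs drive the mean.

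If median regression is kept, restrict it to gymnasts with UI at baseline, obtain standard errors by resampling clubs, and label it as supporting secondary outcome II.

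The cost is one or two sentences and a few lines of Stata code. Data, design, primary analysis and sample size do not change.
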